Due to the high cost involved in conducting clinical caries trials a number of surrogate measures of fluoride efficacy have been introduced. These include in situ caries models, rat caries models, in vitro demineralization and remineralization studies, and fluoride uptake studies. These model systems have been extensively reviewed at a Conference held in Rochester, NY in 1994 (Adv Dent Res 9:169-340, 1995). While intra-oral models have been in use for the past forty years, a "Consensus Conference of Intraoral Models" (ADA, Chicago, Sept. 1990) clearly identified the need for validation of intra-oral caries models for their potential use as methods of evaluating the efficacy of fluoride dentifrices and other fluoride-containing dental products. Based on this conference and the Rochester Models conference, there is general agreement among researchers in the field that appropriately validated in situ models represent an acceptable approach for testing the anticaries potential of fluoride products.

Previous work by our group has shown that a modification of the Koulourides intra-oral model (Koulourides et al., 1974) has sufficient sensitivity and reproducibility to respond in dose-response manner to meet the requirements for model validation (Proskin et al., 1992). The model, which uses partially demineralized enamel as the starting hard tissue substrate, permits the evaluation of the ability of the test dentifrice to enhance net remineralization. Our current model has been validated based on its response to different dentifrice fluoride concentrations - 0, 250, 500 and 1100 ppm fluoride (Zero et al., 1994;

Zero, 1995; Zero et al., 2005) as well as in several more commercially funded in situ studies testing fluoride dentifrice products that also included fluoride dose response controls (unpublished data). An additional capability of the model involves testing the acid resistance of remineralized enamel specimens. This test provides the capability to compare the acid resistance of the mineral deposited during the in situ remineralization phase after treatment with different test products.

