Over the past 10 years we have been experiencing increasing difficulty in recruiting subjects with mandibular partial dentures that meet our inclusion criteria. One of the reasons for the failure is the lack of sufficient room in the posterior buccal flange area of the subjects' partial dentures to accommodate two 4 × 4 mm enamel specimens. In an effort to improve subject recruitment we have redesigned the model so that the enamel specimens (4 mm round) are placed in the posterior denture tooth area of their denture and thus eliminate the requirement for having sufficiently large buccal flange area. We have already identified several potential subjects that only qualify for specimen placement in denture teeth and not in the buccal flange area. We have already successfully conducted an in vitro feasibility exercise to demonstrate the practicality of this technique. Furthermore, we have been placing specimens in the denture teeth location for several other in situ model studies including studies using our new biofilm model and this has not presented to be a problem for the subjects. The alteration of the denture teeth does not affect the occlusal part of the artificial tooth and thus does not alter a functional part of the denture.

An additional aspect of the modified model will be to use bovine enamel and not human enamel as has been our usual practice. We are facing increasing difficulty in obtaining a supply of human teeth for our research studies due to a decreasing supply and anticipated regulatory changes requiring informed consent. Most in situ model systems use either bovine or human teeth as the hard tissue substrate. From the perspective of clinical relevance, human teeth would be the most appropriate to use (Zero, 1995). Bovine enamel are known to have structural and chemical differences and to be more porous than human enamel (Lippert et al., 2013) and it is more vulnerable to acid dissolution than human enamel in an artificial caries model systems (Featherstone & Mellberg, 1981; Lippert et al., 2013; Lippert & Lynch, 2014). However, the resulting lesions are practically indistinguishable from each other (Lippert & Lynch, 2014), and these differences result in quantitative differences and not qualitative differences in their response in in situ model studies (Mellberg, 1992; Lippert & Hara, 2012). Bovine enamel can therefore be considered an acceptable alternative to human enamel.

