7. STATISTICAL ANALYSES AND SAMPLE SIZE JUSTIFICATION

7.1 Statistical Analyses

The mean % SMH recovery will be calculated using the five sets of indentations within each enamel specimen. The mean fluoride uptake will be calculated using the four samples within each enamel specimen. The mean % SMH recovery, mean fluoride uptake, mean acid resistance and mean ΔZ , L, SZ_{max} will be computed for the two enamel specimens within a subject for each specimen location (buccal flange or tooth) by treatment; if a subject is missing an enamel specimen, the available enamel specimen will be used. Analyses of fluoride uptake will be performed after using a natural logarithm transformation because the measurements generally are not normally distributed. The validation of the new model will involve two types of evaluations. 1) Analysis level evaluation: The treatments will be compared using analysis of variance models (ANOVA) suitable for a crossover study. The models will include random effects for subject and fixed effects for study period, product, specimen location, and the location-by-product interaction. The random effects will model the correlation and variances over time within a location and the correlation between locations. The primary comparisons of interest will be to determine if the specimens placed in the tooth find the same comparisons to be statistically significant as the specimens placed in the buccal flange. In addition, although likely to be underpowered, the analyses will also include an evaluation of the equivalence of the two locations. This will involve calculating a 95% confidence interval for the ratio between the tooth and buccal flange locations for the relative difference between treatments (treatment difference divided by the positive control mean). A 5% significance level will be used for all tests. No alpha-level adjustments for multiple comparisons adjustments will be applied. 2) Data level evaluation: Agreement between the data from the tooth and buccal flange locations will be evaluated using Bland-Altman plots and intraclass correlation coefficients (ICCs).

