7.2 Sample Size Justification

Based on previous studies we estimate the standard deviation of the differences between treatments in the crossover model to be 10% for % SMH recovery. With a sample size of 24 subjects completing the study, the study will have 80% power to detect a difference between any two treatments of 6% for % SMH recovery, assuming two-sided tests each conducted at a 5% significance level. Due to expected dropouts during the crossover study, the study will enroll 34 subjects.

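### The primary analysis-level comparison in 7.1 is concordance of significance, which depends on power as well as agreement; the direct between-location contrast on a named endpoint should be primary instead

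*Combined protocol and SAP*

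**What the plan says.** Section 7.1 describes two evaluations for validating the new model.

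The first, at analysis level, is a crossover ANOVA with random subject effects and fixed effects for period, product, location and location-by-product. On the error structure it says: "The random effects will model the correlation and variances over time within a location and the correlation between locations". Its lead question is stated as: "The primary comparisons of interest will be to determine if the specimens placed in the tooth find the same comparisons to be statistically significant"; the reference is the result from the flange specimens. Tests are at 5% without multiplicity adjustment. It then adds that "although likely to be underpowered, the analyses will also include an evaluation of the equivalence of the two locations", by means of a 95% CI for a tooth-to-flange ratio "for the relative difference between treatments (treatment difference divided by the positive control mean").

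The second, at data level, is: "Agreement between the data from the tooth and buccal flange locations will be evaluated using Bland-Altman plots and intraclass correlation coefficients (ICCs").

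No endpoint among those in section 6.4 is named as deciding. Nothing says how many of the six treatment pairs must match. No acceptance limit is given for the ratio, the limits of agreement or the ICC.

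Section 7.2 sizes the study on treatment differences only: with 24 completers and an SD of differences of 10%, "the study will have 80% power to detect a difference between any two treatments of 6% for % SMH recovery". It gives no precision for any comparison between locations.

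**The concern.** Two models can respond identically and still differ in which pairs reach p < 0.05, because each result is subject to chance when power is moderate. Conversely, when the dose effects are large, both models call every pair significant even if one has lost much of its response. The rule can therefore err in both directions, and which error dominates depends on the true dose steps, which the documents do not give.

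This bears on the trial's central question. Section 1 credits the existing model because it "has sufficient sensitivity and reproducibility to respond in dose-response manner to meet the requirements for model validation". A tooth model that has lost sensitivity could still match across 0, 250, 500 and 1100 ppm, and the loss would show only later, when products closer together are compared.

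**Working it through.** **Inputs from the documents.** 24 completers; SD of within-subject treatment differences 10 points for % SMH recovery; two-sided 5% (7.2); four products, hence six pairs (section 4).

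**Assumptions not in the documents.** SD 10 at both locations; equal dose steps; correlation rho between the two locations of 0, 0.5 or 0.9; all six pairs must match (relaxed in step 4).

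**1. The plan's own figure.** Paired t-test, n = 24, difference 6, SD 10, 23 df: power 80.4%. The stated 80% reproduces.

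**2. One pair, by hand.** If two identical, independent models each have power 0.80, they give the same result with probability 0.80² + 0.20² = 0.64 + 0.04 = 0.68. At power 0.50 it is 0.25 + 0.25 = 0.50. Agreement between identical models is thus driven by power.

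**3. All six pairs, by simulation.** 24 subjects × 4 doses × 2 locations; residual SD 10/√2 = 7.07; residual correlation rho between locations; error df (24 − 1)(4 − 1) = 69 per location; a match means the same call in the same direction; 20,000 replicates. Percentage of trials with a full match (three values are rho 0 / 0.5 / 0.9; a range spans them):

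| Flange step (points) | Identical models | Tooth has 60% of response, SD 10 |
|---|---|---|
| 6 | 33 / 48 / 75 | 6 / 12 / 17 |
| 8 | 83–93 | 18–23 |
| 10 | about 99 | about 53 |
| 12 | over 99 | about 81 |
| 15 | over 99 | about 97 |

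**4. A looser rule.** If five of six matches suffice, identical models at 6-point steps pass in 81% / 91% / 98%. The 60% model then passes in 38% / 50% / 55% at 6 points and about 95% at 10. Relaxing the rule exchanges one error for the other.

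**5. Does the planned ratio fill the gap?** For a pair (a, b), with T and F the tooth and flange means, the ratio is [(T_a − T_b)/T_1100] ÷ [(F_a − F_b)/F_1100].
- Uniform loss, every T = 0.6 F: the factor cancels and the ratio is 1.00.
- Slope-only loss of 40%, the same placebo mean m at both locations, flange range 45 points, tooth range 0.6 × 45 = 27: the ratio is 0.6 × (m + 45)/(m + 27). For m = 5: 0.6 × 50/32 = 0.94. For m = 10: 0.6 × 55/37 = 0.89. For m = 30: 0.6 × 75/57 = 0.79. For m = 40: 0.6 × 85/67 = 0.76.

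The undivided ratio of differences is 0.60 in every one of these cases.

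**6. Precision of a direct contrast.** The difference between locations in one treatment difference has SD 10 × √(2(1 − rho)). The 95% half-width is t(23) × SD/√24, with t(23) = 2.069 and √24 = 4.899. For rho 0: 2.069 × 14.14/4.899 = 6.0 points. For rho 0.5: 2.069 × 10/4.899 = 4.2 points.

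**The case against.** **Matching is not the whole validation.** This stands. The Bland-Altman and ICC evaluation is a full second arm, and the interaction and ratio CI are in the first. A reader might infer that the plan contains no direct comparison, or that validation turns on matching alone. Section 7.1 supports neither; the point is confined to what is primary within the analysis-level evaluation.

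**The all-six rule is not in the plan.** This also stands. A reader might take 33% to 75% as the plan's failure-prone pass rate for good models, but the plan states no concordance rule and the figures only illustrate. The 6 points in 7.2 is a detectable difference, not an expected dose step; from 8-point steps the false-failure problem is small. What survives is that loosening the rule lets the 60% model through more often.

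**Quantitative differences are expected.** Section 1 says of bovine and human enamel that "these differences result in quantitative differences and not qualitative differences in their response in in situ model studies", so equal amplitude may not be the aim, and finding the same pairs significant is naturally read as preserved discrimination. That is a fair reading. It argues against prescribing an equal-amplitude margin, but does not make concordance a measure of how well discrimination is preserved.

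**The 60% model does separate these four doses.** True at large steps; the cost falls on later studies with smaller differences.

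**Equivalence would be underpowered.** The plan says so openly. That limits what can be concluded but is no reason to put a less direct comparison first.

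**Conclusion.** The concern holds in this form: the primary analysis-level comparison depends on power as well as on agreement, and no direct between-location contrast on a named endpoint takes its place. Under the stated assumptions the rule can fail identical models (33% to 75% full match at 6-point steps) and pass a model with 60% of the response (81% at 12 points, 97% at 15). Around 8-point steps it separates the two cases well, but the documents give no basis for expecting that size. The rates depend on the assumed step, correlation, SD and matching rule; the dependence on power does not.

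The planned ratio is no substitute: it cannot see a uniform proportional loss and shows a slope-only loss only in part, to a degree set by the placebo mean.

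A reader might go further and conclude that the plan is deficient unless it adopts a formal equivalence margin on amplitude or on discrimination. The documents do not settle which scale matters, and at this sample size identical models could often miss a narrow range, so that is not claimed. Nor is the 80% power figure in error. This should be fixed, but the data to be collected remain suitable for the direct comparison.

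**What to change.** In 7.1:
- Name % SMH recovery, the endpoint behind the sample size, as deciding.
- Make the primary analysis-level result the between-location difference in dose response across all four concentrations (the location-by-dose trend, with the dose scale stated), from the mixed model already planned. Report it with a 95% CI and location-specific SDs, with 1100 versus 0 ppm as a supporting contrast.
- Require alongside it a significant dose trend in the tooth model.
- Make the table of matching significance results descriptive. Keep the ratio CI, Bland-Altman plots and ICCs as planned.

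In 7.2, state the expected precision for the difference between locations in a treatment difference: half-width about 6.0 points at correlation 0 and 4.2 at 0.5 with 24 completers, assuming SD 10 at both locations. These figures are on the amplitude scale only and do not describe precision for discrimination.

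If the sponsor wants a formal validation verdict, it should choose the scale and an acceptance range before unblinding; none is prescribed here.

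The cost is wording: no extra subjects, measurements or change of model. The downside is that the interval may be wide and the result inconclusive if dose steps are small and between-location correlation is low.

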4. TEST TREATMENTS

The following products applied with a provided, marketed toothbrush will be used in this study:

1. 0 ppm F (placebo, negative control)
2. 250 ppm F as NaF (dose-response control)
3. 500 ppm F as NaF (dose-response control)
4. 1100 ppm F as NaF (positive control)

The test products will be provided by GlaxoSmithKline as part of the ISS funding mechanism using their Sensodyne sodium fluoride/silica toothpaste base formulation. The test products and fluoride-free washout toothpaste will be supplied in plain white tubes. Each tube will have a study label affixed. Each study label will contain, but not be limited to, protocol number, product code letter (for treatment products only), directions for storage, emergency contact telephone number and "For Clinical Trial Use Only".

Care should be taken with the supplied study products and their labels so that they are maintained in good condition. It is important that all labels remain intact and legible for the duration of the trial. Subjects should be instructed to not remove or deface any part of the study label.

Subjects will also receive a fluoride-free washout toothpaste and standard toothbrush for home use during the 2 to 3 day lead in period.

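### The primary validation comparison counts joint non-significance as agreement and does not require either location to separate 1100 ppm F from 0 ppm F

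*Combined protocol and SAP*

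**What the plan says.** Section 7.1 describes two kinds of evaluation for validating the modified model (bovine enamel in denture teeth) against the existing one (human enamel in the buccal flange). In the analysis-level evaluation, the comparisons of primary interest are to "determine if the specimens placed in the tooth find the same comparisons to be statistically significant as the specimens placed in the buccal flange". On error rates it says "A 5% significance level will be used for all tests" and "No alpha-level adjustments for multiple comparisons adjustments will be applied".

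Two further evaluations are planned. One is a 95% confidence interval for the tooth-to-flange ratio of relative treatment differences, which the plan itself expects to lack power and for which it gives no margin. The other is Bland-Altman plots and intraclass correlations, without thresholds.

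Section 1 says the existing model "has sufficient sensitivity and reproducibility to respond in dose-response manner to meet the requirements for model validation" and reports that it was validated on the same four fluoride concentrations. Section 4 supplies the controls: "0 ppm F (placebo, negative control"), two dose-response controls at 250 and 500 ppm F, and 1100 ppm F as positive control. No sentence in section 7.1 makes the separation of these controls a condition for interpreting agreement.

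**The concern.** For a given outcome, the primary comparison uses only two lists of significant and non-significant verdicts. Two empty lists are the same list. So the comparison can come out favourably when an outcome did not respond to fluoride at either location, and it then says nothing about whether the modified model works. As written, it also does not ask that a significant difference run the same way at both locations.

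Section 7.1 names % SMH recovery, fluoride uptake, acid resistance, ΔZ, L and SZmax. An outcome with little or no response could be written up as agreeing with the existing model when the trial carries no information on it.

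**Working it through.** **Inputs from the documents.** Four products; 24 completers and SD of treatment differences 10 points for % SMH recovery (section 7.2: "we estimate the standard deviation of the differences between treatments in the crossover model to be 10% for % SMH recovery"); two-sided 5% tests (section 7.2: "assuming two-sided tests each conducted at a 5% significance level"); no multiplicity adjustment (section 7.1).

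**Assumptions.** All six product pairs are compared at each location (inferred from the wording on any two treatments in section 7.2; section 7.1 does not list the pairs). One outcome is considered. The SD is equal at both locations. The residual correlation ρ between locations is 0 to 0.7. A match means that all six verdicts agree.

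**The plan's own figure.** The difference in question is 6 points; section 7.2 states "With a sample size of 24 subjects completing the study, the study will have 80% power to detect a difference between any two treatments of" that size. The standard error is 10/√24 = 2.04 and the noncentrality 6/2.04 = 2.94. A paired t test with 23 df gives 80.4% power, so the figure is reproduced. With the pooled crossover error (23 × 3 − 3 = 66 df) power is 82.5%.

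**No response at either location, closed form at ρ = 0.** For one comparison, the match probability is 0.95² + 0.05² = 0.905. For six, the chance that one location shows nothing significant is the studentized-range probability for 4 means and 66 df at √2 × 1.997 = 2.82, which is 0.800. Both locations empty: 0.800² = 0.64.

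**Simulation with 66 error df, 40,000–80,000 trials per cell.** Equal steps means the same rise from each dose to the next, identical at both locations.

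| True response, both locations | ρ = 0 | ρ = 0.5 | ρ = 0.7 |
|---|---|---|---|
| None: patterns match | 64.5% | 67.7% | 71.6% |
| None: both patterns empty | 64% | 67% | 69% |
| Equal steps of 4 points | 14% | 29% | 39% |
| Equal steps of 6 points | 34% | 48% | 58% |
| Equal steps of 7 points | 62% | 69% | 75% |
| Equal steps of 8 points | 84% | 87% | 89% |
| Equal steps of 10 points | 99% | 99% | 99% |

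At ρ = 0.9 the no-response match rate is 80%. With only the three tests against placebo it is 77%, 80% and 83% for ρ = 0, 0.5 and 0.7; steps of 6 points then give 71%, 79% and 84%, about the same.

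**With the control condition.** Requiring 1100 versus 0 ppm F to be significant at both locations cuts the no-response rate to 0.1%, 0.3% and 0.6% for ρ = 0, 0.5 and 0.7. At 6-point steps the rates stay at 34%, 48% and 58%, because the control contrast is then 18 points and is practically always detected.

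**The case against.** Four points can be made for the plan.

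1. *There is no rule to pass.* Section 7.1 calls the matching of verdicts a comparison of interest, sets other evaluations beside it and defines no decision. That stands: all six verdicts identical is my working definition. The 1100-versus-0 result at each location is also among the planned comparisons, so an empty pattern would be visible. But this is the only evaluation called primary, and nothing says how an empty pattern is to be read.

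2. *The flange model is known to respond.* Section 1 reports validation on the same four concentrations. That makes a trial in which neither location responds less likely. It is not a check within this trial, and section 1 does not say which outcomes the validation covered.

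3. *The failure that matters most is caught.* If the flange responds in 6-point steps and the tooth does not respond, the patterns match in about 0% of studies. That is correct, and the point does not concern that case.

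4. *The planned ratio would expose non-response.* A reader might infer that two unresponsive models would also slip through an acceptance range. The documents do not support this, because the planned measure is a ratio. Treating the positive-control means as equal and known, a 95% Fieller interval for the 1100-versus-0 ratio is bounded only when the flange contrast is itself significant at 5%, so in about 5% of no-response studies. It lies within an illustrative 0.5 to 2 in 0% of them. The ratio thus carries the missing information, but with no margin the plan does not act on it.

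**Conclusion.** The point holds as a gap in wording. The primary comparison can be satisfied by two empty patterns, and no assay-sensitivity condition within the trial prevents it. The size is a match rate of about 64–72% with no response at either location, or 77–83% with tests against placebo only. These figures rest on one outcome, the % SMH recovery SD, 24 completers and ρ of 0 to 0.7. No SD is given for the other outcomes.

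A reader might also infer that the patterns match more often when neither location responds than when both respond identically. That is true at 6-point steps (34–58%), but the order reverses above about 7 points per step (84–99% at steps of 8 to 10). The same happens for responses linear in ppm: 37–63% at a 24-point difference between 1100 and 0 ppm F, 68–81% at 30 and 91–94% at 36. The documents give no expected means, so no general ordering can be claimed. For the same reason one cannot say that the least responsive outcomes are the most likely to be reported as agreeing.

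I rate this a cheap improvement.

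**What to change.** Add to section 7.1: *For each outcome, agreement between locations will be interpreted only if the buccal flange specimens show a significant 1100 versus 0 ppm F difference in the expected direction (5%, two-sided). It will be taken to support the modified model only if the tooth specimens show it too. Otherwise the outcome is reported as not informative (flange fails) or not supported (tooth fails). A comparison counts as the same finding only if it is significant in the same direction at both locations; joint non-significance is reported separately.*

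The expected direction should be written down for each outcome, since ΔZ and lesion depth measure loss while % SMH recovery measures gain.

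The cost is wording only: the planned model already estimates the contrast at each location. The downside falls on weakly responsive outcomes. If the true flange difference between 1100 and 0 ppm F is only 6 points, the outcome is reported as not informative about 18% of the time (1 − 0.825). If the tooth has the same 6-point effect, then at ρ = 0 a further 0.825 × 0.175 = 14% would read as not supported. At a difference of 12 points or more, the flange condition is met essentially always.

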6.2 Lesion Creation

The square and round enamel specimens will be partially demineralized using a modification of the method described by White [1987]. The 4 x 4 mm human enamel specimens will be immersed for 24 and the 4 mm round bovine specimens will be immersed for 18 hours at 37° C under static conditions in 40 ml of an acid buffer (0.05 mol/L lactate), 50% saturated with respect to hydroxyapatite and with 0.2% (wt/vol) carbopol 907 (BF Goodrich Co., USA) added (pH adjusted to 5.0 using KOH), and then rinsed thoroughly with deionized water. The demineralized enamel specimens will then be stored in a moist environment to prevent dehydration.

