6.4.2 Enamel Fluoride Uptake

The microdrill enamel biopsy technique as described by [Sakkab et al., 1984] will be used to analyze the fluoride content of the partially demineralized enamel specimens. Each enamel specimen will be mounted perpendicular to the long axis of a drill bit attached to a specially designed microdrill, and drilled to a depth of ~100 µm through the entire lesion (four cores per specimen; see Figures 2 and 3).

The drilling and sample collection will be performed in a static-controlled atmosphere to prevent loss of enamel powder due to charging effects. The enamel powder sample, pooled from the four drilling samples, will be transferred to an analyzer cup cap. 20 microliters (µl) of 0.5 Molar (M) Perchloric Acid (HClO₄) will be added to the enamel powder and the cap gently swirled to dissolve the powder. To the analyzer cap containing the 20 µl of HClO₄/enamel powder, 40 µl of citrate/ ethylene-diamine-tetraacetic acid (EDTA) buffer and 40 µl of de-ionized water will be added and immediately analyzed for fluoride content using a fluoride specific electrode and pH/Ion meter. The diameter of the drill hole will be determined using a calibrated microscope interfaced with an image analysis system. The amount of fluoride-uptake by enamel will be calculated based on the amount of fluoride divided by the area of the enamel cores and expressed as µg F/cm².

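### Minor: Section 7.1's equivalence ratio, applied literally to log-transformed fluoride uptake, divides a log difference by a log mean and so depends on the overall uptake level at each location

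*Combined protocol and SAP*

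**What the plan says.** Three statements in Section 7.1 bear on this point.

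- Scale for uptake: "Analyses of fluoride uptake will be performed after using a natural logarithm transformation because the measurements generally are not normally distributed".
- Scope of the equivalence work: "the analyses will also include an evaluation of the equivalence of the two locations". It is not limited to particular endpoints, and the plan itself expects low power for it.
- The measure: a 95% confidence interval for the tooth/flange ratio of "the relative difference between treatments (treatment difference divided by the positive control mean". It is defined once for every endpoint.

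The model has "fixed effects for study period, product, specimen location, and the location-by-product interaction". Section 6.4.2 gives the unit of uptake: the fluoride amount is "divided by the area of the enamel cores and expressed as" µg F/cm². On whether the two models should show similar levels, Section 1 says: "Bovine enamel are known to have structural and chemical differences and to be more porous than human enamel". It goes on to expect responses that differ in quantity rather than in kind.

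**The concern.** Dividing a treatment difference by the positive-control mean evidently aims to remove differences in overall level, so that proportional responses can be compared between the two models. That works for an endpoint on its natural scale. On the log scale the treatment difference is already a relative measure, and dividing by the log of the positive-control level brings the level back in. The uptake ratio could then sit away from 1 when both models respond equally, or at 1 when they do not, simply because one location takes up more fluoride overall. The study exists to compare the two models, and this interval is its direct estimate of whether their treatment responses agree in size.

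**Working it through.** **Plan's own figure.** The documents give no figure for the uptake ratio. The only design figure is the power for % SMH recovery in Section 7.2. A paired t-test with n = 24, SD of differences 10, difference 6 and two-sided 5% gives 80.4% power, so the stated 80% reproduces. It does not depend on the issue here.

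**Inputs.** The log scale and the definition of the ratio come from Section 7.1, and the unit from Section 6.4.2. Uptake levels are assumptions. Let F be the flange positive-control geometric mean and kF that of the tooth. Let f_F and f_T be the fold responses (positive control over comparator) in flange and tooth.

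**Literal ratio.** [ln f_T / ln(kF)] / [ln f_F / ln F].

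**Equal fold response.** With f_T = f_F the treatment effect cancels, leaving ln F / ln(kF). At F = 4 and k = 1.5 this is ln 4/ln 6 = 1.386/1.792 = 0.774, whether the common fold is 1.2, 2 or 4. A sound measure would give 1.

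| Tooth/flange level k | F = 2 | F = 4 | F = 8 | F = 16 µg/cm² | Same data in ng/cm² |
|---|---|---|---|---|---|
| 0.8 | 1.475 | 1.192 | 1.120 | 1.088 | 1.030 to 1.024 |
| 0.9 | 1.179 | 1.082 | 1.053 | 1.040 | 1.014 to 1.011 |
| 1.0 | 1.000 | 1.000 | 1.000 | 1.000 | 1.000 |
| 1.1 | 0.879 | 0.936 | 0.956 | 0.967 | 0.988 to 0.990 |
| 1.2 | 0.792 | 0.884 | 0.919 | 0.938 | 0.977 to 0.982 |
| 1.5 | 0.631 | 0.774 | 0.837 | 0.872 | 0.949 to 0.960 |

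The last column multiplies every value by 1000. The ratio moves with the unit in every row except k = 1, where the unit cancels.

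**A real difference can be hidden.** Take F = 4, k = 1.5 and a flange fold of 2. The literal ratio equals 1 when the tooth fold is exp(ln 2 × ln 6/ln 4) = 2.449. The relative-difference ratio from geometric means is then (1 − 1/2.449)/(1 − 1/2) = 0.592/0.5 = 1.18.

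**Check of the alternative.** From geometric means, a contrast with the positive control gives (1 − 1/f_T)/(1 − 1/f_F). This is 1 under equal folds at any level and in any unit. For a contrast between two other products, the requirement is that each product's fold relative to the positive control matches across locations. For example, let the 500 and 250 ppm means be 3 and 2 at both locations, with positive controls of 4 (flange) and 6 (tooth). The ratio is then [(3 − 2)/6]/[(3 − 2)/4] = 0.67, although 500 against 250 ppm is 1.5-fold at both. That is a property of the plan's relative-difference measure, which scales to the positive control.

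**The case against.** The strongest reply is that Section 7.1 never calls for a log mean. It names a relative difference, which naturally means a proportion of the positive-control level, and an analyst could back-transform before forming it. That reading is possible and would remove the problem. It stands as a reason to call this a wording repair, but not as an answer, because the text places uptake analyses on the log scale and makes no exception for the ratio.

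The consequence is also limited. This is one endpoint in an additional analysis with acknowledged low power, and no equivalence margin is stated, so no declared decision turns on the estimate. That stands too, and sets the severity.

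A reader might infer more than the documents support in three places:

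- **That unequal levels are shown.** Section 6.2 says "human enamel specimens will be immersed for 24 and the 4 mm round bovine specimens will be immersed for 18 hours", which may look like evidence of different lesions. But Section 6.4.1 holds all specimens to the same window of 120 ± 20 µm after demineralization, so the shorter bovine immersion is weak support either way. Section 1 makes unequal levels plausible and gives neither size nor direction.
- **That the ratio may turn negative.** It does so if the two control means lie on either side of 1: means of 0.9 and 1.2 µg/cm² give ln 0.9/ln 1.2 = −0.58. Those levels were picked to show the behaviour, and nothing in the documents suggests them.
- **That the result hangs on a choice of unit.** The plan fixes µg F/cm², and the unit matters only when the levels differ. Unit dependence shows that the literal measure is unsound; it is not a separate risk in this trial.

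**Conclusion.** The point holds for the text as written and is minor. Followed literally, Section 7.1 gives an uptake equivalence estimate that mixes the treatment response with the overall uptake level. It is 1 under equal fold response only if the positive-control geometric means of the two locations match.

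The size cannot be fixed from the documents. Under the assumed levels, the departure from 1 runs from about 3% (flange 16 µg/cm², tooth 1.1 times higher) to about 37% or 47% (flange 2 µg/cm², tooth 1.5 or 0.8 times flange). It may be trivial in practice.

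It would be wrong to conclude that the model validation as a whole is compromised. The primary criterion (whether the tooth location finds the same comparisons significant), the Bland-Altman plots, the ICCs and the sample size do not use this ratio. Nor do the endpoints that are not log-transformed share the fault.

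**What to change.** State in Section 7.1 that, for fluoride uptake, the relative difference at each location is formed from back-transformed model means, (GM_a − GM_b)/GM_positive control. The 95% interval for the tooth/flange ratio should come from the delta method or a bootstrap, with the choice named in advance. This is unit-free and keeps the plan's relative-difference measure. It equals 1 when each product's fold relative to the positive control is the same at both locations.

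The back-transformed location-by-product contrast may be reported as a supplement. It should be labelled a ratio of fold-changes, with 1 meaning equal fold response, and not a ratio of effects. If the flange responded 1.2-fold and the tooth not at all, it would read 1/1.2 = 0.83, whereas the geometric-mean relative-difference ratio would be 0.

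The cost is a sentence or two of text, a few lines of code and slightly more work for the interval. No new data, visits or subjects are needed.
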